### **7.8.3 Vital signs**

Only descriptive statistics are planned for this section of the report.

### **7.8.4 ECG**

Clinically relevant abnormal ECG findings will be reported and analysed as AEs.

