5.2.4 Electrocardiogram

The 12-lead ECGs will be performed as scheduled in the [Flow Chart](#). Twelve-lead ECGs (I, II, III, aVR, aVL, aVF, V1 – V6) will be recorded using equipment provided by a central ECG vendor. The ECGs will be recorded for at least 10-second duration after the subjects have rested for at least 5 minutes in a supine position and prior to lab sampling. Electrode placement will be performed according to the method of Einthoven/Goldberger (ankles and wrists). At all time points indicated in the [Flow Chart](#), single ECGs will be recorded. ECG recordings at planned time points may be repeated for quality reasons like alternating current artefacts, muscle movements and electrode dislocation. In this case the repeated ECG recordings will be used if quality was better.

The investigator or a designee will evaluate whether the ECG is normal or abnormal and whether it is clinically significant, if abnormal. The electronic version of the ECG is regarded as source data. Dated and signed printouts will be stored in the patient's medical file if there is no validated and certified e-medical record for ECG data.

Additional ECGs may be collected by the investigator for safety reasons. Clinically relevant findings noticed at baseline assessment (Visit 1) should be reported as baseline condition.

Clinically relevant abnormal findings noticed after baseline assessment will be reported as AEs and followed up and/or treated locally until normal or stable condition.

All ECGs will be transmitted electronically to the central ECG vendor in order to enable a centralized and independent re-evaluation of all 12-lead ECGs. A centralized and independent re-evaluation will be done. Abnormalities detected during this centralized ECG evaluation will not necessarily qualify as AE.

Central evaluation on individual ECG level will be performed by the vendor and a report will be provided to the site. Decisions on eligibility for the trial and treatment or further follow-up of any findings are in the responsibility of the investigator.

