5.2.6 Assessment of adverse events

5.2.6.1 Definitions of AEs

Adverse event

An AE is defined as any untoward medical occurrence in a patient or clinical investigation subject administered a medicinal product and which does not necessarily have to have a causal relationship with this treatment.

An AE can therefore be any unfavourable and unintended sign (including an abnormal laboratory finding), symptom, or disease temporally associated with the use of a medicinal product, whether or not considered related to the medicinal product.

The following should also be recorded as an AE in the eCRF and BI SAE form (if applicable):

- Worsening of the underlying disease or of other pre-existing conditions
- Changes in vital signs, ECG, physical examination and laboratory test results, if they are judged clinically relevant by the investigator*

*Note: If such abnormalities already exist prior to trial inclusion, they will be considered as baseline conditions and should be collected in the eCRF only.

Regarding AEs in the context of suicidal risk assessment by C-SSRS, [Section 5.2.5.2](#) should be adhered.

Serious adverse event

A SAE is defined as any AE which fulfils at least one of the following criteria:

- results in death,
 - is life-threatening, which refers to an event in which the patient was at risk of death at the time of the event; it does not refer to an event that hypothetically might have caused death if more severe.
 - requires inpatient hospitalization or
 - requires prolongation of existing hospitalization,
 - results in persistent or significant disability or incapacity, or
 - is a congenital anomaly / birth defect,
- or
- is deemed serious for any other reason if it is an important medical event when based on appropriate medical judgement which may jeopardise the patient and may require medical or surgical intervention to prevent one of the other outcomes listed in the above definitions. Examples of such events are intensive treatment in an emergency room or at home for allergic bronchospasm, blood dyscrasias or convulsions that do not result in hospitalization or development of dependency or abuse.

Regarding SAEs in the context of suicidal risk assessment by C-SSRS, [Section 5.2.5.2](#) should be adhered.

AEs considered “Always Serious”

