5.7 APPROPRIATENESS OF MEASUREMENTS

All measurements performed during this trial are acceptable measurements in monitoring safety aspects or assessing treatment response in patients with CIAS. In particular, the scheduled safety assessments are appropriate to see drug-induced changes in physical examination, vital signs, ECG and standard laboratory values.

A Phase II study of encenicline (a selective $\alpha 7$ nicotinic acetylcholine receptor agonist) as a treatment for CIAS demonstrated clinically meaningful improvements in cognition and function in patients with Schizophrenia over 12 weeks ([R16-2465](#)). Thus, the treatment period of 12 weeks with BI 425809 is considered to be appropriate to see a change in cognitive function in schizophrenic patients.

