7.3.4 Safety analyses

AEs will be coded using the Medical Dictionary for Drug Regulatory Activities (MedDRA). Standard BI summary tables and listings will be produced. All AEs with an onset between start of treatment and the end of the REP, a period of 11 days after the last dose of trial medication, will be assigned to the on Treatment Period for evaluation.

All treated patients will be included in the safety analysis. In general, safety analyses will be descriptive in nature and will be based on BI standards. No hypothesis testing is planned.

Statistical analysis and reporting of AEs will concentrate on treatment-emergent adverse events, i.e. all AEs occurring between start of treatment and end of the REP. AEs that start

before first drug intake and deteriorate under treatment will also be considered as ‘treatment-emergent’.

Frequency, severity, and causal relationship of AEs will be tabulated by system organ class and preferred term after coding according to the current version of the MedDRA at the database lock.

Laboratory data will be analysed both quantitatively as well as qualitatively. The latter will be done via comparison of laboratory data to their reference ranges. Values outside the reference range as well as values defined as clinically relevant will be summarised. Treatment groups will be compared descriptively with regard to distribution parameters as well as with regard to frequency and percentage of patients with abnormal values or clinically relevant abnormal values.

Vital signs, physical examinations, or other safety-relevant data observed at screening (Visit 1), baseline (Visit 2), during the course of the trial and at the end-of-trial evaluation will be assessed with regard to possible changes compared to findings before start of treatment.

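### The SAP analyses ECGs only through investigator-judged adverse events, so an ECG change below that threshold reaches no visible by-arm summary

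*SAP*

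**What the plan says.** The whole of SAP 7.8.4 reads: "Clinically relevant abnormal ECG findings will be reported and analysed as AEs". It shows no redaction mark and specifies no interval, abnormality category, change from baseline, shift table or by-visit display.

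The protocol assigns the judgement of relevance to the site. Section 5.2.4: "The investigator or a designee will evaluate whether the ECG is normal or abnormal and whether it is clinically significant, if abnormal". Section 5.2.6.1 lists what is to be recorded as an AE, including: "Changes in vital signs, ECG, physical examination and laboratory test results, if they are judged clinically relevant by the investigator".

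In parallel, section 5.2.4 sends all tracings to a central vendor "in order to enable a centralized and independent re-evaluation of all 12-lead ECGs. A centralized and independent re-evaluation will be done". The output described is for the site: "Central evaluation on individual ECG level will be performed by the vendor and a report will be provided to the site". On how these readings relate to AEs it says: "Abnormalities detected during this centralized ECG evaluation will not necessarily qualify as AE".

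Two further protocol passages bear on the point. Section 7.3.4 says that vital signs, physical examinations and a catch-all of other data relevant to safety, from screening through to the end-of-trial evaluation, "will be assessed with regard to possible changes compared to findings before start of treatment". Section 5.7 states that "the scheduled safety assessments are appropriate to see drug-induced changes in physical examination, vital signs, ECG and standard laboratory values".

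**The concern.** The AE rule is a threshold applied to one patient's tracing at a time. It is suited to finding a patient who needs attention. It is not suited to showing a modest change that is common in one arm, because each tracing may look unremarkable alone. Those changes become visible only when values or categories are put together by arm and compared with baseline.

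The trial arranges a standardised second reading of every ECG, yet the visible SAP specifies no summary of those readings. The ECG part of the safety evaluation then rests on separate judgements at about 58 centres (protocol 3.3). Investigators are blinded (protocol 4.1.5.1), so what is at stake is sensitivity to a drug-induced change, not bias between the arms.

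**Working it through.** The plan states no figure for ECG analysis, so there is none to reproduce. The check compares the texts, then counts.

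**1. Follow one post-baseline ECG finding through the documents.**
- The investigator judges it clinically relevant: it becomes an AE (protocol 5.2.4, 5.2.6.1) and enters the AE tables by treatment (SAP 7.8.1).
- The investigator does not judge it clinically relevant, whether or not the central report marks it abnormal: it need not become an AE, and SAP 7.8.4 has no other output. It may appear in subject data listings (SAP 6.7), which are not a comparison by arm.

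**2. Compare ECG with the other safety data in the SAP.**

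| Data | Analysis in the visible SAP |
|---|---|
| Laboratory (7.8.2) | Statistics by visit; shift tables from baseline; extra displays for haemoglobin |
| Vital signs (7.8.3) | Descriptive statistics |
| C-SSRS (7.8.5) | Counts and percentages by arm; shift table |
| PANSS worsening (7.8.5) | Listing of change from baseline, with increases of 5 or more flagged |
| ECG (7.8.4) | AEs only |

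Protocol 7.3.4 says safety analyses follow sponsor standards. The reference list in SAP 9 cites standards for AE analysis, AE dates, PK/PD and laboratory data, but none for ECG, so no cited standard visibly fills the gap.

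**3. Does protocol 7.3.4 reach ECG?** It does not name ECG. However, ECG is a safety assessment under section 5.2, is recorded at the time points that 7.3.4 lists, and is named in 5.7 among the assessments meant to show drug-induced change. The general wording therefore covers it.

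**4. Count the readings.** The flow chart schedules ECGs at Visits 1, 2, 4, 6/EoT and Follow-up. With 200 patients and full attendance:
- all readings: 5 × 200 = 1000
- before treatment (Visits 1 and 2): 2 × 200 = 400
- after baseline (Visits 4, EoT, Follow-up): 3 × 200 = 600, or 300 per arm

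**5. Precision, as illustration only.** The documents give no SD for change in an ECG interval. For an assumed SD, the 95% CI half-width for the difference between arms in mean change is 1.96 × SD × √(2/n), with n per arm.

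| Assumed SD (ms) | n = 100 | n = 90 |
|---|---|---|
| 10 | 2.8 ms | 2.9 ms |
| 15 | 4.2 ms | 4.4 ms |
| 20 | 5.5 ms | 5.8 ms |

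The Treated Set should be close to 100 per arm. The figure of 90 is the evaluable number for the cognitive endpoint after 10% dropout (protocol 7.7) and is shown only for range.

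**The case against.** The strongest reply is that the SAP does what the protocol prescribes. Where the protocol names ECG as an outcome, it uses AEs: the secondary safety endpoint counts clinically relevant ECG abnormalities within (S)AEs (2.1.3, 7.3.2), and 5.2.4 says relevant findings after baseline are reported as AEs. Pre-existing abnormalities are kept apart as baseline conditions, so the AE route already contains some notion of change. This stands. A reader might infer that the SAP breaches a protocol promise, but 7.3.4 neither names ECG nor commits to a by-arm table of central readings.

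A reader might also infer that the central readings go unused, or that ECG findings are never compared between arms. The documents do not support either inference. The vendor's report goes to the site and can inform the investigator's decision. Findings that become AEs are tabulated by treatment, and listings are planned. What remains is narrower: findings that do not become AEs have no visible summary by arm.

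Three further points limit the weight:
- The visible protocol describes no cardiac or QT signal for the drug (1.4), lists only hepatic injury as an AESI (5.2.6.1), and has no QTc-based eligibility or withdrawal rule. Nothing here suggests that an effect exists or would be missed.
- Physical examination, which 7.3.4 does name, also has no summary of its own in the visible SAP. Reliance on AEs is thus not peculiar to ECG. Unlike physical examination, though, ECG has a standardised central reading that lends itself to a summary.
- Protocol 5.2.3 says the central laboratory transfers its results to the sponsor. For ECG, 5.2.4 mentions only the report to the site. Whether numeric readings reach the sponsor is not stated.

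Parts of the SAP are redacted, so an ECG summary elsewhere cannot be excluded.

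**Conclusion.** The point holds as a reporting gap in the safety analysis. AE reporting of ECG findings is consistent with the protocol but, as the only analysis, gives no visible by-arm view of change from before treatment. Up to 600 post-baseline central readings, with 400 pre-treatment readings to compare them with, have no specified summary; both counts assume full attendance.

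The half-widths should not be read as evidence that an effect would be missed. They rest on assumed SDs and show only that a descriptive comparison could be informative if numeric intervals are available. The conclusion also assumes that no redacted part of the SAP contains an ECG summary. Safety analysis stays descriptive, with no test implied, and the primary efficacy analysis is untouched. This is a modest, inexpensive improvement.

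**What to change.** Keep the existing sentence in SAP 7.8.4 and add a descriptive summary on the Treated Set, by arm and nominal visit, of the central ECG results that the vendor supplies:
- where results are numeric, values and change from Visit 2
- a shift table of the central normal/abnormal interpretation, from baseline to post-baseline

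State which visit serves as baseline. Protocol 5.2.4 treats Visit 1 as baseline when deciding whether an ECG finding is an AE, whereas SAP 6.7 uses Visit 2 with screening as the fallback.

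If the sponsor prefers not to summarise these data, the SAP should say so, give the reason, and reconcile it with protocol 7.3.4 and 5.7.

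The cost is a few additional tables to produce and review. If not already arranged, a transfer of the vendor's data to the sponsor would also be needed, and this should be confirmed first. No extra visit, patient or ECG recording is required.

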### **7.8.5 Others**

#### Worsening Disease State as assessed by PANSS

Change in PANSS from baseline to each post-baseline visit will be presented in a data listing. Increases greater than or equal to 5 will be flagged.

#### Suicidality as assessed by the C-SSRS

C-SSRS will be summarized by counts and percentages per treatment group. The number of patients with suicidal ideation (for each type of 1 to 5 separately), suicidal behaviour (type 6 – 10), and with self-injurious behaviour without suicidal intent will be presented, overall and within subcategories. A summary will also be presented for lifetime experience. Shift table and listings will be provided.

[figure not shown]
## **8. TIMEPOINT OF RELEASE OF TREATMENT INFORMATION**

The treatment information will be released to unblind the trial database after the last patient has completed their End-of-Study/Follow-up visit and all data has been entered and cleaned as defined in the “Data Ready to be Unblinded and/or Final Trial Closure Notification” (RUN) form.

## 11. HISTORY TABLE

Table 11: 1 History table

Version	Date	Author	Sections changed	Brief description of change
1	10-OCT-2022		None	This is the final TSAP

